# **8 DATA COLLECTION, STUDY MONITORING, AND CONFIDENTIALITY**

## **8.1 Data Collection**

Data for this study will be managed by the Neuropsychology Research Team in the Department of Epidemiology and Cancer Control. Data collected at baseline and follow-up assessments will be entered by optical scanning. The optical scanning program has the capacity for designer specific error checks, flagged at the time the questionnaires are scanned. After data are scanned, they are processed and converted into a SAS (Cary, NC) format where a second error check is completed. Data from neurocognitive tests are double-entered into a separate secure Access database and compared for accuracy. All data mismatches will be reviewed by two members of the survey center staff and compared to the original documents (when applicable) for resolution. NIH Toolbox data will be stored on remote computer servers and will be completely de-identified. Data from the tDCS mobile units and the cognitive training (Lumosity) will be downloaded and processed by the study team using software provided by the product manufacturers.

## **8.2 Study Monitoring**

The study team will hold monthly meetings and review case histories or quality summaries on participants. The PI and study team will be responsible for ensuring protocol compliance. Continuing reviews by the IRB and CT-SRC will occur at least annually.

This study is associated with an Investigational Device Exemption (IDE) and will be monitored by the St. Jude Clinical Research Monitors accordingly. The monitors will review up to 15% of the study participants semi-annually for appropriateness of the informed consent process, eligibility, adverse event recording and participant's status. Additional information may be monitored at the request of the Internal Monitoring Committee (IMC), the IRB, or other institutional administration.

Source document verification of eligibility and informed consent for 100% of St. Jude participants will be performed by the Eligibility Coordinators within 5 working days of completion of enrollment. The Clinical Research Monitor will review all SAE reports and other applicable essential regulatory documentation. The Monitor will generate a formal report which is shared with the Principal Investigator (PI), study team, and the Internal Monitoring Committee (IMC).

### **8.3 Confidentiality**

Confidentiality will be maintained. Data forms will be kept in locked file cabinets, in locked offices, accessed only by study staff on an "as needed" hierarchical basis. All electronic files will be stored on a password protected computer and identifying information will be stored in separate electronic files and linked by participant number. Data files downloaded for statistical analyses will not contain personal identifiers.

The medical records of study participants may be reviewed by the St. Jude IRB, FDA, clinical research monitors, etc.

## **9 STATISTICAL CONSIDERATIONS**

The sample size justification will be based on evaluating the primary objective, as that objective is the basic design of how the intervention will be delivered in a subsequent randomized controlled trial should this pilot study prove feasible. We will consider the trial to be feasible if at least 50% of the survivors are able to complete 5 sessions (tDCS along with cognitive stimulation) successfully out of 10. Any participant who completes Phase I,

but is unwilling to participate in Phase II due to the tDCS procedure will be counted towards failure. In the testing of hypothesis framework we would like to test the null hypothesis  $H_0: P \leq 0.5$  vs.  $H_1: P > 0.7$ . Then, using Simon's two-stage Minimax design with type I error rate  $\alpha=0.05$  and power  $(1-\beta)=0.8$  we have the following stopping rules. As an additional measure of feasibility, the consent rate must be  $>50\%$  among all participants approached to participate. Study staff will track study enrollment, and the study statistician will make the determination for study continuation.

In the first stage we will recruit 23 survivors and if the number of survivors who complete at least 5 sessions is at least 13 then we will proceed to the next stage and recruit an additional 14 survivors and if at least 24 survivors out of 37 complete at least 5 sessions then the tDCS trial would be considered feasible. However, since we expect that roughly 20% of the survivors may not initiate the trial after leaving the institution (i.e. may not provide any information at all for objective 1.1.1) we anticipate replacing these survivors and, thus, a total of 45 survivors will be needed for evaluating the Phase II objective. Participant accrual will cease when 37 participants agree to participate in Phase II.

With 37 survivors recruited for phase I of the study, we will have roughly 97.7% power for objective 1.2.1 to detect an improvement of 0.65 in standardized units, respectively, with type I error  $\alpha=0.05$ .

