### **Analysis:**

Objective 1.1.1: The feasibility of the 5-week tDCS intervention will be evaluated using Simon's two stage Minimax design with stopping rules described above.

Objective 1.2.1: The improvement in scores on symbol digit coding, Stroop test, shifting attention test, digit span and verbal fluency from baseline to 5-week follow up will be done using matched pair one sample t-tests. In addition, the improvement in EF measures over the 5 week period will also be evaluated using longitudinal methods and implemented using PROC MIXED or PROC GEE in SAS 9.3.

Objective 1.2.2: The improvement in the scores on the NIH Toolbox Card Sort, Flanker and Working Memory tasks between tDCS and sham, will be done using matched pair one sample t-test.

It will be important to monitor for AEs in both phases of the study as well. Thus, in an "ad hoc" manner using one sided 95% confidence bounds we will monitor for all grade 3 or higher adverse events (All types of AE's included)

which are related to study interventions. Among the 45 patients enrolled in the study, if at any time point at least 5 patients ( $\geq 5$ ) have grade 3 or higher toxicity, the 95% lower confidence limit would be 0.059 suggesting that the true AE rate could be higher than 5% which would be unacceptable, the feasibility of the 5 week intervention would be questionable and a consideration will be given to stop or amend the trial.

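### Section 9 words the primary feasibility criterion as at least 50% completing, which contradicts the Simon boundary (13 of 23, then 24 of 37) that the plan uses to decide it

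*Combined protocol and SAP*

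**What the plan says.** Section 9 (Statistical Considerations) gives the criterion for the primary objective twice.

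- First, in words: "We will consider the trial to be feasible if at least 50% of the survivors are able to complete 5 sessions", out of the 10 planned.
- Then as a test. The null is a completion rate of at most 0.5, the alternative is a rate above 0.7, alpha is 0.05 and power is 0.8, "using Simon's two-stage Minimax design with type I error rate" control as stated. The resulting rule has two steps. Stage 1 enrols 23 participants, and its continuation condition reads: "if the number of survivors who complete at least 5 sessions is at least 13 then we will proceed to the next stage". After 14 more participants, "if at least 24 survivors out of 37 complete at least 5 sessions then the tDCS trial would be considered feasible".

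The Analysis subsection, under Objective 1.1.1, refers only to the second form: "The feasibility of the 5-week tDCS intervention will be evaluated using Simon's two stage Minimax design with stopping rules described above".

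Section 9 also sets a further feasibility condition, a consent rate above 50% among those approached. It gives the study statistician the decision on whether the study continues.

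**The concern.** Both sentences state when the trial is to be called feasible, on the same endpoint, with different thresholds: 50% and 64.9%. They also treat a 50% rate in opposite ways. The first sentence includes 50% among the feasible results, while the null hypothesis classes it as unacceptable.

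Section 9 links this objective to a later randomised trial, so the criterion is a go/no-go rule. If a pre-specified sentence appears to allow 51% to 62% to be reported as feasible, the decision can be argued either way once the data are known. The stated type I error of 0.05 belongs to the Simon boundary and does not carry over to a 50% cut-off.

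**Working it through.** **Inputs (all from section 9).** Null rate p0 = 0.5; alternative p1 = 0.7; alpha 0.05; power 0.80; stage 1 n1 = 23, continue at 13 or more; stage 2 n2 = 14, total 37; feasible at 24 or more.

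**Formula.** With X1 ~ Bin(23, p) and X2 ~ Bin(14, p) independent, the probability of passing stage 1 and reaching a total of at least r is

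S(r, p) = Σ over x = 13 to 23 of P(X1 = x) × P(X2 ≥ r − x).

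**Step 1: reproduce the plan's design.** S(24, 0.5) = 0.0482 and S(24, 0.7) = 0.8011, so the stated alpha and power are met. A full search over two-stage designs finds 37 to be the smallest total size that meets both. Among designs with n = 37, this one has the smallest expected size under the null: 23 + (1 − 0.661) × 14 = 27.7, where 0.661 is the probability of stopping at stage 1. Lowering the final boundary by one gives S(23, 0.5) = 0.088, so 24 cannot be relaxed.

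**Step 2: where the two statements differ.**

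- Half of 37 is 18.5. So 18/37 = 48.6% fails a 50% cut-off and 19/37 = 51.4% meets it.
- 23/37 = 62.2% and 24/37 = 64.9%. The statements therefore disagree at 19, 20, 21, 22 and 23 completers.
- At stage 1, 12/23 = 52.2% is above 50%, yet the rule stops the trial.

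**Step 3: operating characteristics of each reading.**

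| Rule | Type I error at 0.5 | Power at 0.7 |
|---|---|---|
| 13/23, then 24/37 (Simon, as planned) | 0.048 | 0.801 |
| 13/23, then 19/37 (50% cut-off, stage 1 look kept) | 0.299 | 0.945 |
| 19/37 with no stage 1 look | 0.500 | 0.995 |

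**Step 4: how often the disputed zone would occur.** The joint probability of passing stage 1 and finishing at 19 to 23 is S(19, p) − S(24, p):

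| True rate | S(19, p) | S(24, p) | Joint probability of 19–23 | Probability of passing stage 1 | Conditional on passing |
|---|---|---|---|---|---|
| 0.5 | 0.299 | 0.048 | 0.25 | 0.339 | 0.74 |
| 0.6 | 0.700 | 0.329 | 0.37 | 0.713 | 0.52 |
| 0.7 | 0.945 | 0.801 | 0.14 | 0.945 | 0.15 |

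At a true rate of 0.6, three outcomes are possible: 19 to 23 (0.37), 24 or more (0.33), and stopping at stage 1 or finishing below 19 (1 − 0.700 = 0.30). The disputed zone is the most likely of the three.

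**The case against.** The best defence is that 50% is a benchmark for the underlying rate, not an observed cut-off. Section 9 carries the same figure straight into the null hypothesis and derives the boundaries from it, and the Analysis subsection names only the Simon rule. On this view 24 of 37 implements the benchmark. The one-sided exact 95% lower bound (simple binomial) is 0.5005 for 24/37 and 0.473 for 23/37, so 24 is the smallest count that shows a rate above 50%. The type I errors of 0.30 and 0.50 then belong to rules that the plan does not prescribe.

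Most of this stands. A reader might infer that the plan leaves two decision rules of equal standing, so that 19 to 23 completers would be both feasible and not feasible. The documents do not support that: anyone applying the Analysis subsection would conclude not feasible. Nor do they support the inference that the design or the sample size is wrong.

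The defence does not make the opening sentence correct. It is phrased as a condition for declaring feasibility. Nothing says that it refers to a population rate or that it yields to the later boundary. Even as a statement about the true rate it includes 50%, which the null excludes. That last clash concerns a single parameter value and changes no boundary, but it shows that the sentence does not match the hypothesis under either reading.

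**Conclusion.** The point holds as an error in the wording of the primary success criterion. The Simon design, its boundaries and its size are sound, and the Analysis subsection makes them the operative rule. The opening sentence contradicts that rule at 19 to 23 of 37, and at 12 of 23 in stage 1. If it were used as an observed cut-off, type I error would rise from 0.048 to 0.30 with the stage 1 look kept, or to 0.50 without it. The disputed results are not remote, with joint probabilities of 0.25, 0.37 and 0.14 at true rates of 0.5, 0.6 and 0.7.

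These figures assume independent participants with a common completion rate and exactly 23 and 37 evaluable participants. The sentence should be corrected, because it concerns the primary objective and the correction is trivial.

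**What to change.** Replace the opening criterion in section 9 with wording such as:

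*A completion rate of 50% or less is unacceptable. Session completion will be judged adequate only if at least 13 of the first 23 participants, and then at least 24 of 37, complete at least 5 of the 10 sessions; no other session-completion threshold applies. In addition, the consent rate among those approached must exceed 50%.*

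The last sentence is needed. Without it, meeting the Simon boundary would appear to suffice for feasibility, which would conflict with the consent condition in the same section.

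The cost is a short rewording. Sample size, boundaries, conduct and analysis stay as they are. The visible bar for session completion becomes 64.9%, which the design already requires.

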#### **4.2.2 Transcranial Direct Current Stimulation – Mobile System:**

The mobile transcranial direct current stimulation system is manufactured by Soterix Medical and consists of a battery pack, control unit and a self-positioning headband with sponges. Participants will be given the device after completing the clinical portion of the study and trained in correct usage. Participants will complete two stimulation sessions per week for 5 weeks. The sessions will provide 1 mA DC for 15 minutes in the same manner as the clinical system. Participants will be supplied iPads for the cognitive stimulation training, and the iPad will be used to monitor correct tDCS usage. The tDCS unit requires a unique code for each stimulation session. Study staff will use video conferencing to confirm correct electrode placement, then provide the code to initiate treatment. Each session will be monitored for compliance and to assess any adverse events.

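### Section 9 applies the number 37 to groups that cannot coincide, so the 13/23 and 24/37 feasibility rule has no single analysis set

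*Combined protocol and SAP*

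**What the plan says.** All of the following is in Section 9, Statistical Considerations, unless noted.

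- The final decision: "if at least 24 survivors out of 37 complete at least 5 sessions then the tDCS trial would be considered feasible". The first look requires 13 of the first 23.
- Refusers: a Phase I completer who "is unwilling to participate in Phase II due to the tDCS procedure will be counted towards failure".
- Home non-starters: the plan expects that "roughly 20% of the survivors may not initiate the trial after leaving the institution", and continues: "we anticipate replacing these survivors and, thus, a total of 45 survivors will be needed for evaluating the Phase II objective".
- End of accrual: "Participant accrual will cease when 37 participants agree to participate in Phase II".
- A separate criterion on consent: "As an additional measure of feasibility, the consent rate must be" above 50% of those approached.

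The Analysis subsection adds nothing on who is counted. For Objective 1.1.1 it refers back to the "two stage Minimax design with stopping rules described above". On timing, Section 4.2.2 states: "Participants will be given the device after completing the clinical portion of the study and trained in correct usage". Section 4.2.3 likewise describes people finishing Phase I and continuing to Phase II before home training begins.

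**The concern.** A two-stage binomial rule has its stated error rates only for one fixed set of people. Section 9 uses 37 in two ways that pull apart: as the denominator of the rule after non-starters have been replaced, and as the number whose agreement closes accrual. Someone who agrees, takes the device home and never starts has already used one of the 37 places. The refusers raise the opposite problem: they must be in the denominator as failures, but by definition they did not agree.

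Section 9 makes this result the basis for a later randomised trial. Two analysts following the text could apply 24/37 to different people and reach different conclusions. Followed literally, the accrual stop could also fail an intervention that meets the design alternative among those who start. Separately, replacement narrows what the result describes, and the plan does not say so.

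**Working it through.** **Inputs (Section 9).** p0 = 0.5; p1 = 0.7; alpha 0.05; power 0.8; n1 = 23, continue at ≥13; n = 37, success at ≥24; non-starting about 20%; total 45.

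**1. The plan's own rule.** P(pass | p) = Σ over x = 13 to 23 of Bin(x; 23, p) × P(X2 ≥ 24 − x | 14, p).
- p = 0.5: 0.0482. p = 0.7: 0.8011.
- A search for the Minimax design with these inputs returns the same boundaries.
- The total of 45 follows from 37 × 1.2 = 44.4, rounded up. It allows 45 − 37 = 8 replacements (8/45 = 17.8%).

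The boundaries are therefore right for a fixed 37.

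**2. Accrual stop against replacement.** Assume that agreement comes before going home.
- Starters among 37 who agree: 37 × 0.8 = 29.6, so 29 or 30.
- Share of starters needed to reach 24: 24/30 = 80%; 24/29 = 83%.
- P(X ≥ 24 | 30, 0.7) = 0.160; P(X ≥ 24 | 29, 0.7) = 0.093. These use the final threshold only and ignore the first look.
- Cross-check, letting the number of starters vary: each of the 37 completes with probability 0.8 × 0.7 = 0.56, and the full two-stage rule gives 0.175.

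All are far below the planned 0.80. If the analyst instead uses about 30 as the denominator, Section 9 has no cut-off for it.

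**3. Refusers against the 37 who agree.** If k refusers are added to 37 who agree, the denominator is 37 + k. The documents do not give k, so it is an assumption here. Keeping 24 as the threshold, single-stage, at p = 0.5:

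| k | Denominator | P(X ≥ 24) |
|---|---|---|
| 2 | 39 | 0.100 |
| 4 | 41 | 0.174 |
| 8 | 45 | 0.383 |

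So 24 cannot be carried over to a larger set.

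**4. What replacement makes the result describe.** With non-starters replaced, P is completion among starters plus tDCS refusers. Take a bare pass with 8 replaced:
- 24/37 = 64.9%.
- 24/45 = 53.3%, exact (Clopper-Pearson) 95% CI 37.9% to 68.3%, if all 45 enrolled belong in the wider denominator.

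**5. Effect of classing non-starters as tDCS failures.** Let d = 8/45 not start, let a share s of them be tDCS-related, and let 70% of starters complete. The success rate in the set is 0.7(1 − d)/(1 − d(1 − s)). The share s is not in the documents, so the full range is shown.

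| s | Rate in set | P(pass), two-stage |
|---|---|---|
| 0 | 0.700 | 0.80 |
| 0.5 | 0.632 | 0.48 |
| 1 | 0.576 | 0.23 |

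**The case against.** The best defence is that Section 9 can be read sensibly: tDCS refusers are failures, other non-starters are replaced, and 37 is the evaluable count. Replacement is disclosed, and restricting the question to people who start is a legitimate choice. This stands, but it does not rescue the accrual sentence, which counts agreement rather than evaluable participants. It would do so only if agreeing meant starting at home, which is nowhere stated and sits badly with the order of events in Sections 4.2.2 and 4.2.3.

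Four stronger readings are tempting and are not supported:

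- *Replacement breaks the type I error.* With 8 of 45 replaced and 50% completion over everyone, the rate among starters is 0.5/(1 − 8/45) = 0.608 and the rule passes with probability 0.37. But that 50% refers to a wider population than the plan's null covers once non-starters are replaced. For the set after replacement, alpha is 0.048 as planned.
- *A non-starter whose reason is tDCS is left unclassified.* The refuser sentence turns on unwillingness because of tDCS and is not limited to refusal in the clinic. On its ordinary reading such a person is already a failure. Saying so explicitly is a clarification.
- *The missed-appointments provision in Section 6.1 removes starters from the analysis.* That section lists off-study criteria, not analysis exclusions, and Section 9 replaces only people who do not initiate. Nor is every such person a failure: anyone with five or more sessions done has met the endpoint.
- *The 45 are all people who took the device home.* The synopsis and the Analysis text treat 45 as total enrolment, and refusers after Phase I may be among them. The 53% figure therefore depends on the assumption stated with it.

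**Conclusion.** The concern holds as a conflict within Section 9. Non-starters cannot be replaced once 37 have agreed, and tDCS refusers cannot sit both inside the rule's denominator and among 37 who agree. At the plan's own 20%, the accrual stop leaves about 30 starters, and the chance of reaching 24 at a true 70% falls to 0.09 to 0.16. This rests on agreement preceding the return home, which the documents suggest but do not state.

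The Simon arithmetic is correct and replacement is acceptable. What is missing is a statement that the feasibility conclusion leaves out replaced non-starters, a real limitation for a home-based intervention. The consent-rate criterion does not fill that gap, because it measures agreement among those approached and not starting at home. Section 4.2.3 says that adherence to training will be examined, but does not promise completion over a wider denominator. This should be fixed before the rule is applied.

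**What to change.** In Section 9:

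1. Define one evaluable set, in enrolment order, for both looks (23, then 37): participants who start at home, plus Phase I completers unwilling to go on because of tDCS, whether they say so before or after going home. The latter are failures under the existing sentence.
2. Make the accrual stop refer to 37 in that set instead of 37 who agree.
3. State that every starter stays in the set and is classed by the existing endpoint: five or more of ten sessions is a success, fewer is a failure. This includes anyone taken off study for missed appointments.
4. State that the 24/37 conclusion excludes replaced non-starters.
5. Beside it, report completion over all Phase I completers offered Phase II, with an exact interval, counting non-starters as 0 of 10 sessions and tDCS refusers as failures. The zero is observable: each session needs a code issued by staff, and the training program logs use.

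**Cost.** The 13/23 and 24/37 cut-offs do not change. Each non-starter's reason must be recorded. The second figure will be less favourable (for example 53% beside 65%). Each non-starter classed as a tDCS failure lowers the chance of passing, from 0.80 to 0.48 or 0.23 if half or all of 8 in 45 are so classed and 70% of starters complete.

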### **Analysis:**

Objective 1.1.1: The feasibility of the 5-week tDCS intervention will be evaluated using Simon's two stage Minimax design with stopping rules described above.

Objective 1.2.1: The improvement in scores on symbol digit coding, Stroop test, shifting attention test, digit span and verbal fluency from baseline to 5-week follow up will be done using matched pair one sample t-tests. In addition, the improvement in EF measures over the 5 week period will also be evaluated using longitudinal methods and implemented using PROC MIXED or PROC GEE in SAS 9.3.

Objective 1.2.2: The improvement in the scores on the NIH Toolbox Card Sort, Flanker and Working Memory tasks between tDCS and sham, will be done using matched pair one sample t-test.

It will be important to monitor for AEs in both phases of the study as well. Thus, in an "ad hoc" manner using one sided 95% confidence bounds we will monitor for all grade 3 or higher adverse events (All types of AE's included)

which are related to study interventions. Among the 45 patients enrolled in the study, if at any time point at least 5 patients ( $\geq 5$ ) have grade 3 or higher toxicity, the 95% lower confidence limit would be 0.059 suggesting that the true AE rate could be higher than 5% which would be unacceptable, the feasibility of the 5 week intervention would be questionable and a consideration will be given to stop or amend the trial.

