### 1.2 Secondary Objectives

- 1.2.1 To estimate the efficacy of a tDCS intervention paired with cognitive stimulation.

Hypothesis 2: The home-based tDCS and cognitive training intervention will result in improved executive function in adult survivors of childhood after a five week intervention.

- 1.2.2 To explore the short-term effect of tDCS on measures of executive function among adult survivors of childhood ALL participating in the SJLIFE study.

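### The 5% error rate and 97.7% power stated for objective 1.2.1 are those of one paired t-test, but the plan tests five scores with no adjustment or success rule

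*Combined protocol and SAP*

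**What the plan says.** Section 1.2 lists objective 1.2.1 as secondary and words it as estimating efficacy. It attaches one directional hypothesis: "The home-based tDCS and cognitive training intervention will result in improved executive function".

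Section 9 (Statistical Considerations) claims, for 37 survivors and a type I error of 0.05, "roughly 97.7% power for objective 1.2.1 to detect an improvement of 0.65 in standardized units". It does not say whether the test is one- or two-sided, or which score the 0.65 refers to.

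The Analysis paragraph of Section 9 then spreads the objective over five outcomes: "The improvement in scores on symbol digit coding, Stroop test, shifting attention test, digit span and verbal fluency", where the change "from baseline to 5-week follow up will be done using matched pair one sample t-tests". It continues: "In addition, the improvement in EF measures over the 5 week period will also be evaluated using longitudinal methods", using a mixed model or GEE in SAS. Those measures are not listed.

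Section 9 states no deciding outcome, composite, testing order, multiplicity adjustment or number of tests that must succeed. It does not say which method decides if the two disagree.

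Section 5.2.4 gives the battery used before and after Phase II: Digit Span, Verbal Fluency, Oral Trail Making and the CCSS Neurocognitive Questionnaire. Of the five analysed scores, only digit span and verbal fluency are in it.

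**The concern.** An alpha and a power are properties of a decision rule. Here they are attached to an objective with one hypothesis, but the plan supplies five tests and no rule for turning five results into one conclusion. The stated pair (0.05, 97.7%) cannot hold under either obvious rule. If any one significant score supports the hypothesis, the error rate is not 0.05. If all five must be significant, the power is not 97.7%.

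What is at stake is how the efficacy signal is read. With no rule fixed in advance, one nominally significant score out of five could be reported as improved executive function and carried into the planning of the later randomised trial with more confidence than the data justify. The unsettled outcome list adds room to choose after the data are seen.

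**Working it through.** **Inputs.** From Section 9: n = 37, standardised improvement 0.65, alpha 0.05, five scores, paired t-tests. The documents give no correlation among the five change scores, so it is an assumption and a range is shown. All figures take 37 complete pairs, as the plan's own figure does.

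**1. Reproduce the stated power.** For one paired test, two-sided 0.05, normal approximation: Φ(0.65 × √37 − 1.96) = Φ(3.954 − 1.960) = Φ(1.994) = 97.69%. This matches 97.7%. The noncentral t gives 97.0%. One-sided 0.05 gives 98.95% (normal) or 98.7% (t). The plan's figure is therefore the power of one test using the whole 0.05, most plausibly two-sided.

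**2. Error rate if any one of five counts and nothing has changed.** For independent scores:
- either direction, two-sided 0.05: 1 − 0.95⁵ = 22.6%
- improvement only, two-sided 0.05: 1 − 0.975⁵ = 11.9%

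For correlated scores, five equicorrelated paired t-tests were simulated (n = 37, 40,000 replicates):

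| Assumed correlation | Two-sided 0.05, either direction | Two-sided 0.05, improvement only | One-sided 0.05 |
|---|---|---|---|
| 0 (exact) | 22.6% | 11.9% | 22.6% |
| 0.3 | 21.3% | 10.8% | 19.4% |
| 0.5 | 18.2% | 9.0% | 16.5% |
| 0.7 | 15.3% | 7.6% | 13.7% |
| 0.9 | 10.5% | 5.2% | 9.8% |
| One test only | 5% | 2.5% | 5% |

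**3. Power if all five must succeed.** With every score truly improving by 0.65 and each tested at two-sided 0.05, independence gives 0.970⁵ = 86%. Simulation gives 88% at correlation 0.3 and 89% at 0.5.

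**4. If the family shrinks to the two scores found in both lists.** The either-direction rate is 1 − 0.95² = 9.8% if independent, and 9.1% by simulation at correlation 0.5.

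**5. The second method.** On complete pre/post pairs a mixed model should essentially reproduce the paired t-test and add almost nothing. A GEE z-test with an uncorrected robust standard error, counted as an alternative route to significance on all five scores, would raise the either-direction rate to 26.7%, 25.3% and 22.4% at correlations 0, 0.3 and 0.5.

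**6. Power after adjustment.** Holm tests the smallest of five p-values at 0.05/5 = 0.01 and the rest at larger levels, so per-test power is at least that at 0.01: 88.4% (t), or Φ(3.954 − 2.576) = 91.6% (normal). With two tests the first step is 0.025, giving Φ(3.954 − 2.241) = 95.7% (normal).

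**The case against.** The strongest reply is that this is a pilot. Objective 1.2.1 is secondary and worded as estimation, the sample size rests on feasibility, a randomised trial is meant to follow, and the continuation rules in Section 9 use session completion, consent rate and adverse events, not cognitive scores. Strict familywise control is often not asked of such an objective. Phase II also has no control arm, so even a perfectly controlled test could not attribute a pre/post change to the intervention. All of this stands, and it limits the severity. It does not remove the point: the same plan attaches a directional hypothesis, an alpha, a power and significance tests to this objective, and a plan that tests should say what counts as success.

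A reader might infer that the objective's false-positive rate simply is 18–23%. The documents do not support that as a fact. It needs an any-one-of-five rule, which the plan never states; correlations between 0 and about 0.5, which the plan does not give; and rejections counted in either direction, although the hypothesis is about improvement.

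A reader might also infer that each of the five scores is tested twice on the same two time points, making ten looks. The text says only that executive-function measures over the five weeks will be modelled. It neither lists all five nor limits the data to two visits, and Section 4.2.3 describes per-session training records that could be an input.

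Finally, the size of the family is itself unsettled, because three of the five scores are missing from the Section 5.2.4 battery. That is correct, and it makes reconciling the lists the first step.

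**Conclusion.** The point holds in a conditional form. The 0.05 and 97.7% describe one two-sided paired t-test at n = 37, not objective 1.2.1 as the plan would test it. Their distance from the objective's true operating characteristics depends on a rule the plan does not state:

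- Any one of five counts: two-sided familywise error up to 22.6%, falling to about 18% at correlation 0.5 and 15% at 0.7. Counting only false improvement, it is about 9–12% at correlations 0 to 0.5, against 2.5% for one test.
- All five must succeed: power of about 86–89% if every score moves by 0.65.
- Only the two scores common to both lists are tested: two-sided error of at most 9.8% for independent or positively correlated scores.

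If alpha was meant as one-sided 0.05, the any-one rate for false improvement is 16.5–22.6% at correlations 0.5 to 0. The stated power fits the two-sided reading better.

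This is a minor-to-moderate point. The consequence is over-reading of a secondary efficacy signal in an uncontrolled pilot; the feasibility test is unaffected and no go/no-go decision turns on it.

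**What to change.** In Section 9:

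1. Reconcile the five scores in the Analysis paragraph with the pre/post battery in Section 5.2.4, and list the outcomes that will have both assessments.
2. For any claim under Hypothesis 2, apply Holm across the paired t-tests on that list. Alternatively, name in advance one deciding outcome or one composite and test it once at 0.05. A composite is a matter of judgement: it can dilute an effect confined to one skill, and on the Section 5.2.4 battery it would mix a self-report questionnaire with performance tests.
3. State that the longitudinal model is supportive only, and name its outcomes, time points and method.
4. State the sidedness, and restate 97.7% as the power of a single test at two-sided 0.05. If five tests are kept, add that power is about 88% per test at 0.01.

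The change is to wording only and needs no new data or participants. The cost is somewhat lower per-test power: from 97.0% to 88.4% on the t calculation with five tests, and a smaller loss if the reconciled list is shorter.
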